7.4 Routine Adverse Event Reporting

All Adverse Events **must** be reported in routine study data submissions. **AEs reported through CTEP-AERS must also be reported in routine study data submissions.**

Adverse event data collection and reporting, which are required as part of every clinical trial, are done to ensure the safety of patients enrolled in the studies as well as those who will enroll in future studies using similar agents. AEs are reported in a routine manner at scheduled times during the trial using Medidata Rave. For this trial the Adverse Event is used for routine AE reporting in Rave.

7.5 Secondary Malignancy

A *secondary malignancy* is a cancer caused by treatment for a previous malignancy (e.g., treatment with investigational agent/intervention, radiation or chemotherapy). A secondary malignancy is not considered a metastasis of the initial neoplasm.

CTEP requires all secondary malignancies that occur following treatment with an agent under an NCI IND/IDE be reported via CTEP-AERS. Three options are available to describe the event:

- Leukemia secondary to oncology chemotherapy (e.g., acute myelocytic leukemia [AML])
- Myelodysplastic syndrome (MDS)
- Treatment-related secondary malignancy

Any malignancy possibly related to cancer treatment (including AML/MDS) should also be reported via the routine reporting mechanisms outlined in each protocol.

7.6 Second Malignancy

A second malignancy is one unrelated to the treatment of a prior malignancy (and is **NOT** a metastasis from the initial malignancy). Second malignancies require **ONLY** routine adverse event reporting unless otherwise specified.

8. PHARMACEUTICAL INFORMATION

A list of the adverse events and potential risks associated with the investigational administered in this study can be found in Section 7.1.

8.1 MLN0128 (TAK-228) (NSC # 768435)

Other Names: MLN0128, INK128, NSC# 768435

Classification: mTOR inhibitor, TORC1/2

CAS Registry Number: 1224844

Molecular Formula: C₁₅H₁₅N₇O **M.W.:** 309.3

Approximate Solubility: MLN0128 (TAK-228) exhibits a pH-dependent aqueous solubility: at physiological pH the solubility is approximately 0.1 mg/mL and at or below pH 3 the solubility is greater than 15 mg/mL.

Mode of Action: MLN0128 (TAK-228) is a non-rapamycin analog mTOR (mechanistic target of rapamycin) kinase inhibitor. The mTOR kinase regulates cell growth, translational control, angiogenesis, and cell survival by integrating nutrient and hormonal signals. The mTOR complex (TORC) is an intracellular point of convergence for a number of cellular signaling pathways. MLN0128 (TAK-228) is a potent and selective adenosine tri-phosphate (ATP)-competitive inhibitor of mTOR complex 1 and 2 (TORC1/2).

Description: MLN0128 (TAK-228) drug substance is a white to off-white, crystalline powder.

How Supplied: MLN0128 (TAK-228) is supplied by Millennium Pharmaceuticals, Inc. and distributed by the Pharmaceutical Management Branch, CTEP/DCTD/NCI as size 2 hard gelatin capsules in the following strengths: 1 mg (white opaque color) and 3 mg (orange opaque color). The composition of the drug product consists of a blend of MLN0128 (TAK-228) drug substance, microcrystalline cellulose, and magnesium stearate. **Milled** formulations will have a white label with a large watermark of the strength on the label.

MLN0128 (TAK-228) capsules are packaged in 30-count, 60-cc high-density polyethylene (HDPE), white, opaque, round, tamper- and child-resistant bottles.

Storage: Capsules are to be stored in the original package between 15°C to 30°C, with allowed short-term excursions between 2°C and 40°C.

Route of Administration: Orally, given 2 hours before or 1 hour after a meal. Do not chew, open or manipulate the capsule in any way prior to swallowing. Each dose should be taken with 8 ounces (240 mL) of water.

Potential Drug Interactions: Multiple human metabolizing enzymes are involved in the Phase I metabolism of MLN0128 (TAK-228). When normalized for human liver content, the CYP isoforms CYP3A4, CYP2C9, and CYP2C19 appear to contribute to MLN0128 (TAK-228) metabolism. MLN0128 (TAK-228) displayed low potential ($IC_{50} > 25 \mu M$) for inhibition of the major human CYP isoforms.

Patient Care Implications: Women of childbearing potential should use effective methods of contraception during and through 90 days after the last dose of MLN0128 (TAK-228). Men should use effective methods of contraception and not donate sperm during and through 120 days after the last dose of MLN0128 (TAK-228).

Availability

MLN0128 (TAK-228) is an investigational agent supplied to investigators by the Division of Cancer Treatment and Diagnosis (DCTD), NCI.

MLN0128 (TAK-228) is provided to the NCI under a Collaborative Agreement between the Pharmaceutical Collaborator and the DCTD, NCI (see Section 12.3).

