A significant and meaningful difference in tolerability was observed in the comparison of the MTDs between unmilled and milled MLN0128 (TAK-228) when administered QD. This difference in tolerability may be possibly explained due to the effect of food on the safety/tolerability of unmilled MLN0128 (TAK-228) in study IND128-001. The GastroPlus™ simulation performed on study suggests that under fasting conditions, unmilled and milled MLN0128 (TAK-228) administrations result in comparable exposures to MLN0128 (TAK-228); whereas in the fed state, milled MLN0128 (TAK-228) resulted in higher C_{max} (1.5- to 2-fold higher) and earlier T_{max} than unmilled MLN0128 (TAK-228) with comparable AUCs. Consequently, a dose of 3 mg QD was chosen as the RP2D of milled MLN0128 (TAK-228) dose in empty stomach conditions.

The RP2D for milled MLN0128 (TAK-228) on a weekly schedule was determined to be 30 mg, the same weekly RP2D as seen for the older unmilled formulation. Six patients treated at 30 mg weekly with the milled formulation did not demonstrate any DLT, but the agent was not escalated further. No DLT had been demonstrated for milled MLN0128 (TAK-228) at the prior 20 mg QW dose as well.

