considered. Oral sulfonylureas (e.g., glipizide or glyburide) should be used with caution, due to the higher risk of inducing hypoglycemia in patients. The dose of oral hypoglycemic agents should be adjusted in patients with renal insufficiency. In addition, patients should be encouraged to follow a low carbohydrate diet once hyperglycemia is first observed.

If any fasting serum glucose reading performed at the site indicates hyperglycemia ($>$ ULN or ≥ 110 mg/dL), the study staff should first confirm that the patient was fasting at the time of blood specimen collection (ie, nothing by mouth for at least 8 hours before collection).

In-Home Daily Fasting Glucose Monitoring

In addition to obtaining fasting glucose levels at the clinic visits as outlined in the Schedule of Events, all patients receiving TAK-228 will be given a glucometer to monitor their daily fasting blood glucose levels at home. The level should be collected daily, predose on dosing days, and at approximately the same time each day.

On Cycle 1 Day 1, the patient will be provided an in-home glucometer. Patients should be trained on proper use of the glucometer and instructed to collect a daily fasting blood glucose level every morning (predose on dosing days), starting on Cycle 1 Day 2. Patients will be instructed to bring the glucometer with them to each study visit so that the data collected can be reviewed and recorded in the source documents. Investigators will be responsible for reviewing the home glucose monitoring logs for hyperglycemia.

The patient will be instructed to contact the site immediately if the value is abnormal (ie, ≥ 150 mg/dL) for further instructions on the management of their hyperglycemia. Hyperglycemia observed during home glucose monitoring should be confirmed in the clinic.

If no irregularities in the fasting blood glucose level are observed during a minimum of 2 consecutive months, then the frequency of in-home fasting blood glucose testing can be reduced to a minimum frequency of once weekly, depending on the investigator's judgment and approval. Patients will continue to notify the investigator of fasting blood glucose levels that exceed 150 mg/dL and, if blood glucose levels are not well controlled or if the patient requires either oral hypoglycemic agents or insulin to control blood glucose levels, then the frequency of in-home testing of fasting blood glucose levels will be reinstated to daily.

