9.2.2 MLN0128 (TAK-228) Pharmacokinetics – Plasma

9.2.2.1 Patient Considerations

Patients participating in this study will be asked to provide blood samples during Cycle 1 of treatment. The morning dose of MLN0128 (TAK-228) must not be given until after pretreatment blood draw.

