9.2.2.2 Blood Collection Schedule

Blood samples (6 ml) will be drawn in green top sodium heparin tubes 30 minutes before drug administration on Days 1, 2 and 8, and at the following times after administering the oral dose on Day 1 and 8: 30 min, 1 hr, 2 hrs, 3 hrs, 4 hrs, and 8 hrs. Thus, 15 samples will be collected for a total of 90 ml whole blood. Note that the windows for the pk samples are \pm 10 min for the 30 minutes pre-drug sample; \pm 5 minutes for the 30 minute and 1 hour post-drug samples; \pm 10 min for 2 hours post-drug sample and \pm 15 min for the 3, 4 and 8 hour post-drug samples. It is more important to record time accurately than to perform the blood drawn exactly at the scheduled time.

Note: The physical exam and labs performed on Cycle 1 Day 1 may be performed the day prior in order to begin the pharmacokinetic sample collection early enough on Cycle 1 day 1 that an 8 hour pk sample is possible. If an 8 hour pk draw is not possible, please collect a 7 hour or a 7 $\frac{1}{2}$ hour sample and note the timepoint on the label of the tube and a collection draw worksheet.

Please complete the pk sample blood draw list in Appendix D and include a copy with the samples at shipment.

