APPENDIX B: STUDY MEDICATION CALENDAR

STUDY # _____

Patient's Name _____ Cycle # _____ Day 1 of Cycle _____ / _____ / _____ PATIENT ID # _____

INSTRUCTIONS:

- The capsules are to be swallowed intact, not less than 2 hours before or 1 hour after a meal. Do not chew, open or manipulate the capsule in any way prior to swallowing. Each dose should be taken with 8 ounces (240 mL) of water. Doses are to be taken at about the same time each day. If a dose is missed, it can be taken up to 6 hours past the scheduled time. If more than 6 hours past the scheduled time, the dose should not be taken and will not be made up. Vomited doses will not be made up.
- Please record the times that you take your study medications. Return this diary and the medication bottles (even if unopened or empty) along with any unused pills at your next visit.

| DAY OF WEEK:
_____ |
|--|--|--|--|--|--|--|
| Day 1 of Cycle
Pills: _____
____ :____ AM or PM | Day 2 of Cycle
Pills: _____
____ :____ AM or PM | Day 3 of Cycle
Pills: _____
____ :____ AM or PM | Day 4 of Cycle
Pills: _____
____ :____ AM or PM | Day 5 of Cycle
Pills: _____
____ :____ AM or PM | Day 6 of Cycle
Pills: _____
____ :____ AM or PM | Day 7 of Cycle
Pills: _____
____ :____ AM or PM |
| Day 8 of Cycle
Pills: _____
____ :____ AM or PM | Day 9 of Cycle
Pills: _____
____ :____ AM or PM | Day 10 of Cycle
Pills: _____
____ :____ AM or PM | Day 11 of Cycle
Pills: _____
____ :____ AM or PM | Day 12 of Cycle
Pills: _____
____ :____ AM or PM | Day 13 of Cycle
Pills: _____
____ :____ AM or PM | Day 14 of Cycle
Pills: _____
____ :____ AM or PM |
| Day 15 of Cycle
Pills: _____
____ :____ AM or PM | Day 16 of Cycle
Pills: _____
____ :____ AM or PM | Day 17 of Cycle
Pills: _____
____ :____ AM or PM | Day 18 of Cycle
Pills: _____
____ :____ AM or PM | Day 19 of Cycle
Pills: _____
____ :____ AM or PM | Day 20 of Cycle
Pills: _____
____ :____ AM or PM | Day 21 of Cycle
Pills: _____
____ :____ AM or PM |
| Day 22 of Cycle
Pills: _____
____ :____ AM or PM | Day 23 of Cycle
Pills: _____
____ :____ AM or PM | Day 24 of Cycle
Pills: _____
____ :____ AM or PM | Day 25 of Cycle
Pills: _____
____ :____ AM or PM | Day 26 of Cycle
Pills: _____
____ :____ AM or PM | Day 27 of Cycle
Pills: _____
____ :____ AM or PM | Day 28 of Cycle
Pills: _____
____ :____ AM or PM |

Patient's Signature _____

Date _____

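### The 3 mg daily dose was chosen for an empty stomach, but the dosing rule allows a capsule 1 hour after any meal, PK doses carry no food condition, and the visible forms record no meal time (minor)

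*Combined protocol and SAP*

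**What the plan says.** - **Dose rationale (Section 2.2.7).** After a tolerability difference between the milled and unmilled forms, "a dose of 3 mg QD was chosen as the RP2D of milled MLN0128 (TAK-228) dose in empty stomach conditions". Section 5 uses that dose as the starting dose, on days 1 to 21 of each 28-day cycle.
- **Meal rule (Section 8.1).** "Orally, given 2 hours before or 1 hour after a meal". Appendix B gives patients the same interval: "not less than 2 hours before or 1 hour after a meal". Neither limits the size of the meal. Section 5.1.1, on agent administration, adds no food condition.
- **PK doses (Section 9.2.2).** The morning dose "must not be given until after pretreatment blood draw", and that draw is scheduled "30 minutes before drug administration on Days 1, 2 and 8", with a tolerance of plus or minus "10 min for the 30 minutes pre-drug sample". The section has no food or fasting instruction.
- **Records.** Each Appendix B diary cell holds a pill count and a clock time. The Appendix D sheets hold scheduled and actual times for the samples and the dose.
- **Fasting rules that do exist.** These concern glucose. Section 5.2 defines fasting as at least 8 hours with nothing by mouth and tells patients to "collect a daily fasting blood glucose level every morning (predose on dosing days), starting on Cycle 1 Day 2". The chemistry panel in the Section 10 footnotes includes a fasting glucose.

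**The concern.** Whether the stomach is empty at dosing depends on the time since the last meal, and that is the shorter of the two stated intervals: 1 hour. A patient who follows the rule exactly can take the capsule, and have a PK profile drawn, in a food state that the dose rationale may not cover and that the visible forms cannot show afterwards.

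The protocol itself treats food state as relevant. Section 2.2.7 reports that the formulations were studied fasted and fed, offers food as a possible reason for the tolerability difference, and then attaches a food condition to the dose.

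The PK data also have a stated job. Section 2.4.1 wants them to help explain differences in toxicity and response. Section 9.1.1.2 plans Cmax, Tmax, half-life and accumulation and, if the data allow, a mixed-effects model of variability within and between patients. If food affects absorption of this capsule, an uncontrolled and unrecorded meal adds variability to Cmax and Tmax that those analyses could not separate from other sources. Meal times that are not written down on the day are hard to recover later.

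**Working it through.** No power or error-rate figure is involved. The check compares the texts, with a little arithmetic on time windows and form rows.

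**1. The plan's sample count.** Section 9.2.2.2 has predose draws on 3 days and 6 post-dose draws on each of 2 days: 3 + (6 × 2) = 15 samples, and 15 × 6 ml = 90 ml. Both match the stated figures.

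**2. What the Appendix D sheets hold.**

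| Sheet | Sample rows | Dose rows | Meal rows |
|---|---|---|---|
| Cycle 1 Day 1 | 7 | 1 | 0 |
| Cycle 1 Day 2 | 1 | 1 | 0 |
| Cycle 1 Day 8 | 7 | 1 | 0 |
| Total | 15 | 3 | 0 |

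All 15 samples are covered and no sheet has a place for food. The 28 daily cells of the diary have none either.

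**3. What the predose draw protects.** The draw is 30 ± 10 minutes before the dose, so 20 to 40 minutes before it. Take the 1-hour rule as running from the end of a meal (an assumption, because the text does not say). The last permitted meal then ends at least 60 minutes before the dose.

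- Latest meal end, draw 40 minutes before the dose: 60 − 40 = 20 minutes before the draw.
- Latest meal end, draw 20 minutes before the dose: 60 − 20 = 40 minutes before the draw.

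A meal between draw and dose is therefore barred, but a meal that ended 20 to 40 minutes before the draw is permitted.

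**4. What the fasting glucose protects.** A home reading before the dose makes a fasted dose more likely. It does not require one: a patient may test, eat, and take the capsule an hour later within the rules. Home testing starts on Day 2. On Day 1, Section 10 includes fasting glucose in the chemistry panel but allows labs to be drawn the day before, and the visit grid is not legible enough to confirm when the panel applies. Food state is thus likely to be fasted on many PK mornings, but it is fixed by rule on none of them.

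**5. The rationale beside the rule.** Section 2.2.7 attaches an empty-stomach condition to the dose. Section 8.1 and Appendix B agree with each other on 2 hours before or 1 hour after a meal. No visible text says that the second is meant to satisfy the first.

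**The case against.** The strongest reply is that nothing here is inconsistent. Section 8.1 and Appendix B match, the protocol never defines an empty stomach, and the 2-hour/1-hour interval may be exactly how the supplier put that condition into practice. The fasted and fed studies named in Section 2.2.7 could support it, but their food-effect results are not reproduced. This stands. That 1 hour after a large meal is not clearly an empty stomach is a clinical inference, not a stated conflict. A reader might also infer that the two intervals were transposed; nothing in the documents shows that.

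Second, the record is only partly visible. Appendix C, the eCRFs and the collection worksheet mentioned in Section 9.2.2.2 cannot be read here, and one of them may capture meals. This also stands, so the point covers only the diary and the Appendix D sheets.

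Third, a reader might take the 1.5- to 2-fold higher Cmax in Section 2.2.7 as the size of the problem. It is not. That figure is a simulated comparison of milled with unmilled drug in the fed state, with comparable AUC. It is not a fed/fasted ratio for the capsule used here, and the food explanation offered there concerns the unmilled form.

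Fourth, a reader might infer a bias in accumulation, with Day 1 possibly fed and Day 8 fasted. The documents do not support that. It would pair the worst case on one day with an assumed best case on the other. A fasting glucose may apply on Day 1 as well, a patient can eat after testing on Day 8, and the plan does not say that accumulation comes from the two full profiles rather than from predose samples.

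Finally, PK is a tertiary objective and Section 13.4.6 makes the correlative analyses descriptive. That limits the severity. It does not make the missing instruction useful to leave out.

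**Conclusion.** The point holds as a minor one. Following the plan exactly can produce PK profiles in a food state that is neither fixed by Section 9.2.2 nor recorded on the visible forms, while the dose itself was stated for an empty stomach.

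The effect on exposure or toxicity cannot be quantified, because the documents give no fed/fasted result for the milled capsule. No contradiction, direction of harm or accumulation bias is claimed. What is affected is how well the tertiary PK results, mainly Cmax and Tmax, can be interpreted, and how closely dosing matches the condition in Section 2.2.7. The CR/CRi decision rule, significance level, power and sample size do not depend on it.

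The conclusion rests on two assumptions: that a dose 1 hour after a meal of any size may not be an empty-stomach dose, and that no document outside the visible text already fixes or records food state on PK days.

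**What to change.** 1. In Section 9.2.2.1, require the Cycle 1 Day 1 and Day 8 PK doses to be taken fasted, using the 8-hour definition already in Section 5.2.
2. Add a row for the time of the last meal to each of the three Appendix D sheets, and use it when interpreting Cmax and Tmax. It can also be a candidate covariate if the mixed-effects model is run.
3. Confirm the intended meal interval with the supplier. Then reword Section 8.1 and Appendix B, and any food instruction in Appendix C, to a window that secures an empty stomach, for example at least 2 hours after and 1 hour before a meal.

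The cost is three form rows, one added sentence in Section 9.2.2.1, wording changes in two or three other places and one query. Dosing becomes slightly stricter for patients, and those on glucose-lowering drugs need the usual care while fasting on the two PK mornings. No visits or samples are added.

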8.2 Agent Ordering and Agent Accountability

8.2.1 NCI-supplied agents may be requested by the Principal Investigator (or their authorized designee) at each participating institution. Pharmaceutical Management Branch (PMB) policy requires that agent be shipped directly to the institution where the patient is to be treated. PMB does not permit the transfer of agents between institutions (unless prior approval from PMB is obtained). The CTEP-assigned protocol number must be used for ordering all CTEP-supplied investigational agents. The responsible investigator at each participating institution must be registered with CTEP, DCTD through an annual submission of FDA Form 1572 (Statement of Investigator), Curriculum Vitae, Supplemental Investigator Data Form (IDF), and Financial Disclosure Form (FDF). If there are several participating investigators at one institution, CTEP-supplied investigational agents for the study should be ordered under the name of one lead investigator at that institution.

In general, sites may order initial agent supplies when a subject is being screened for enrollment onto the study.

Active CTEP-registered investigators and investigator-designated shipping designees and ordering designees can submit agent requests through the PMB Online Agent Order Processing (OAOP) application (<https://eapps-ctep.nci.nih.gov/OAOP/pages/login.jspx>). Access to OAOP requires the establishment of a CTEP Identity and Access Management (IAM) account (<https://eapps-ctep.nci.nih.gov/iam/>) and the maintenance of an “active” account status and a “current” password. For questions about drug orders, transfers, returns, or accountability, call or email PMB anytime.

8.2.2 Agent Inventory Records – The investigator, or a responsible party designated by the investigator, must maintain a careful record of the receipt, dispensing and final disposition of all agents received from PMB using the appropriate NCI Investigational Agent (Drug) Accountability Record Form (DARF) available on the CTEP forms page. Store and maintain separate NCI Investigational Agent Accountability Records for each agent, strength, formulation and ordering investigator on this protocol.

9. BIOMARKER, CORRELATIVE, AND SPECIAL STUDIES

9.1 Biomarker Studies

9.1.1 Plasma Pharmacokinetics

9.1.1.1 Hypothesis and Rationale

Hypothesis: In those patients with inadequate drug exposure, inhibition of 4EBP1 phosphorylation and other cellular effects of mTOR dual inhibitors assayed as described in Sections 9.1.2-9.1.6 will be limited.

Rationale: These studies are necessary to characterize the pharmacokinetics of MLN0128 (TAK-228) in patients with acute lymphoblastic leukemia and to assess pharmacodynamic relationships with phosphorylated mTOR substrates and expression levels of BCL2L11 (Bim), BBC3 (Puma), MCL1 and BCL2.

